10.2 Data Management

An Excel key will be created by the study coordinators with study ID (random alphanumeric code) to identify patients, saved in a secure folder on a UNC SOD server. This linkage file will be stored separately from data and destroyed at the close of the study and will never be shared beyond the study coordinators.

All data collected from participants and results from sample analysis will be coded with unique numerical identifiers and stored in the UNC CDART clinical research database and on a secure UNC-CH server. Only trained, IRB-approved study personnel will enter and access data in the secure CDART research database.

Consented patients' data (including screening questions, demographics, and the survey on mouth rinse acceptability) will be collected using the CDART dental toolkit program, which stores data on a secure UNC maintained server and meets federal guidelines for clinical study data acquisition. Only HIPAA and human subjects trained, IRB-approved study personnel will collect, enter and manage patient data; study coordinators will serve in this capacity.

Data will be collected in the CDART research database using participant's study ID and no other PHI identifiers, on approved, carefully designed digital forms within CDART. CDART forms will include questions with drop downs, radio button multiple choice and text field entry, depending on the question type. There will be separate digital forms for inclusion/exclusion screening questions (before sample collection begins), demographic

questions, and questions regarding mouth rinse experience (taste, color, sensation) and willingness to use a mouth rinse in various settings (e.g. dentist or doctor appointments). A separate linkage file, securely stored on UNC servers, will be utilized to associate the random alphanumeric study ID with patient identifier, so samples and CDART data will not be associated with patient identifiers.

Data will only be transmitted among the research team using the SOD secure research server. Demographic data will be transmitted among the research team through access to the secure CDART research database system, stored on secure UNC servers, which study personnel will access only through encrypted computers via secure user account.

Linkage files containing identifiers will be deleted and permanently removed from all servers and study computers at the conclusion of the study with acceptance of associated manuscripts. Saliva specimens will be labeled with a study ID (random alphanumeric code) that is not identifiable without the linkage file, and therefore will not be identifiable after linkage file destruction.

The quality control committee (described below) will be in charge of monitoring these forms and the CDART database.

10.3 Quality Assurance

The Clinical Quality Management Plan (CQMP) establishes the quality management guidelines this study, also referred to as *MOR2*. The purpose of the CQMP is to identify and document the ongoing processes and activities that will be used to monitor and facilitate quality protocol execution following study initiation. Quality measures related to study development and start-up are not included in this plan. An individual who has no other role on the study team will be responsible for execution of this plan.

QM Activity Schedule and Tools

Quality Management (QM) activities will be conducted for each enrolled study subject. Additional QM activities and reviews will be conducted on an as-needed basis in response to staff or process changes.

The site Quality Assurance Coordinator (QAC) will use the Quality Management Subject Data Review Tool to review completion and accuracy of the source documents, eCRFs and Delegation of Responsibility (DOR).

The following outlines the QM process:

- The QAC will maintain the CQMP and QM tools/logs in electronic folder.
- The QAC will review 100% of the executed consents using the QM Subject Data Review Tool. The QAC will verify form completion and accuracy and verify that the most current IRB-approved study consent documents are being used.
- The QAC will review 100% of CDART eCRF data. This includes all eCRF records containing CRF and/or source documentation. The QAC will verify completion of study data entry, subject dispositions and if any unanticipated problems, adverse events,

promptly reportable events and/or protocol deviation have been documented and reported to local IRB as required by the UNC Office of Research Ethics.

- The QAC will review completion of the Delegation of Responsibilities (DOR) prior to study start and upon new study personnel.
- At an interval of 10 enrolled subjects, the QAC will randomly select one subject and review all source documentation and any other corroboration documentation for eCRF data entry, all eCRF's and pregnancy log (if applicable).
- This CQMP will be a living document and will be reviewed for applicability and accuracy and updated as necessary by the QAC. Upon each review, the QAC will provide the study team feedback and report items covered by the review, identification of problem areas and trends, suggest corrective action plan(s) (if applicable), and if/when there is a need for revision to CQMP. Additional QM needs identified will be communicated to the study team where needed and revisions made upon request of the Investigator.

10.3.1 Training

All study personnel have been trained in health privacy (HIPAA) and human subjects research through the CITI program and are certified to work with patient data on clinical trials. Study coordinators and healthcare providers are trained in and approved for the use of the CDART electronic research database and EPIC medical record system. Technical research personnel performing viral PCR and infectivity assays are approved to operate in their BL3 laboratory facilities and have specialized, lab-based training in these molecular techniques. They have also undergone training in the use of universal precautions and management of human biological samples along with bloodborne pathogen training. Finally, the GoHealth Clinical Research core has highly experienced research coordinators who will monitor all study staff to ensure protocol compliance and quality assurance.

10.3.2 Quality Control Committee

Findings of the site Quality Assurance Coordinator (QAC) will be presented to the investigators and study coordinators (as appropriate for the findings) at selected weekly meetings for discussions and remediation actions as appropriate. There is only one site for this study. The use of on-label, widely used mouth rinses (like Listerine) and collection of saliva carry minimal risk for participants, apart from the very rare, undiagnosed allergy, which would be managed through proper referral to the neighboring UNC hospital. Therefore, there is no study quality control committee.

10.3.3 Metrics

Every salivary sample will be collected in a conical tube with millimeter markings to monitor salivary volume. If insufficient saliva is collected, the study personnel collecting

the samples from participants will note insufficient volume in the CDART database for each applicable time point and will indicate in CDART if the subject must be withdrawn and replaced. If a patient is unable to generate sufficient saliva for the 0 min, 15 minutes or 30 minutes post-rinse time points, the subject will be removed from the study and this will be noted in CDART along with their insufficient samples. If a subject is unable to generate sufficient saliva for time points 45 or 60 minutes post-rinse, the patient will remain in the study but their insufficient samples will be noted in CDART.

For RT-PCR and viral infectivity assays, all salivary samples will be run in triplicate with standard experimental controls (negative and positive) and protocol quality checks performed by research technical personnel in the COVID core, [name], [name] and [name] laboratories.

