6.2.5 Completion/Final Evaluation

This study requires only one 70-90 minute, single visit appointment. After consenting and randomization, subjects will be asked to rinse with an unlabeled/blinded antiviral mouth rinse for 60 seconds and provide 5 mL of saliva prior to the rinse and 2 mL of saliva immediately post-rinse, 15 minutes post-rinse, 30 minutes post-rinse, 45 minutes post-

rinse, and 60 minutes post-rinse. Subjects will also be asked to complete a short survey about the rinsing experience.

Subjects may withdraw from the trial at any time at their own request, or they may be withdrawn at any time at the discretion of the Investigator or Sponsor for safety, behavioral or administrative reasons.

The Investigator may discontinue a subject if, in the opinion of the Investigator, the subject is no longer a suitable candidate for the study. Possible reasons for the discontinuation of a subject are including but not limited to: adverse event, protocol deviation, missed appointment, subject no longer meets the eligibility criteria.

Patients may be removed from the study due to an allergic reaction to a mouth rinse or due to failure or inability to comply with study procedures.

If a patient suffers from severe xerostomia/dry mouth, such that s/he cannot produce the baseline salivary sample volume or the immediate, 15 minute and 30 minute post-rinse saliva volumes, s/he will be removed from the study with a parking voucher, but without a gift card and will be replaced. If a patient suffers from dry mouth, such that s/he cannot produce salivary sample volumes needed for later time points (45 minutes or 60 minutes post-rinse) but s/he produced sufficient baseline, immediate, 15 minute and 30 minute post-rinse samples, s/he will still be compensated with a gift card and parking vouchers, and will remain in the study. Missing or deficient salivary samples will be noted in CDART. Severe xerostomia is an exclusion criteria during screening, yet we anticipate that some individuals may not know that they have severe xerostomia until they are participating in the study visit and then need to discontinue due to reduced salivary flow, as described.

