8. INTERVENTION DISCONTINUATION

Subjects may withdraw from the trial at any time at their own request, or they may be withdrawn at any time at the discretion of the Investigator or Sponsor for safety, behavioral or administrative reasons.

The Investigator may discontinue a subject if, in the opinion of the Investigator, the subject is no longer a suitable candidate for the study. Possible reasons for the

discontinuation of a subject are including but not limited to: adverse event, protocol deviation, missed appointment, subject no longer meets the eligibility criteria.

Patients may be removed from the study due to an allergic reaction to a mouth rinse or due to failure or inability to comply with study procedures.

If a patient suffers from xerostomia/dry mouth, such that s/he cannot produce the baseline salivary sample volume or the immediate, 15 minute and 30 minute post-rinse saliva volumes, s/he will be removed from the study with a parking voucher, but without a gift card and will be replaced. If a patient suffers from dry mouth, such that s/he cannot produce salivary sample volumes needed for later time points (45 minutes or 60 minutes post-rinse) but s/he produced sufficient baseline, immediate, 15 minute and 30 minute post-rinse samples, s/he will still be compensated with a gift card and parking vouchers, and will remain in the study. Missing or deficient salivary samples will be noted in CDART.

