9.3 Definition of Populations

Our population includes patients 18-65 years old who have tested positive with COVID-19 in the prior 10 days, and/or have symptom development in the prior 10 days (for symptomatic participants). Inclusion and exclusion criteria (described elsewhere) will be met. We are not treating patients for their COVID-19 infection.

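### Participants already randomised and rinsed are removed and replaced if saliva is short at 0, 15 or 30 minutes, and no analysis set of all randomised participants who rinsed is defined

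*Combined protocol and SAP*

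**What the plan says.** **Order of events.** Section 6.2.5: "After consenting and randomization, subjects will be asked to rinse with an unlabeled/blinded antiviral mouth rinse for 60 seconds". Section 9.2 also places assignment after consent and screening, and before the rinse is handed over.

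**Removal and replacement.** Section 8 covers a participant who "cannot produce the baseline salivary sample volume or the immediate, 15 minute and 30 minute post-rinse saliva volumes, s/he will be removed from the study". Section 6.2.5 carries the same rule and adds that the person leaves with a parking voucher "but without a gift card and will be replaced". Section 10.3.3 gives the post-rinse rule as "0 min, 15 minutes or 30 minutes post-rinse time points, the subject will be removed from the study", and the staff collecting samples "will indicate in CDART if the subject must be withdrawn and replaced".

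**Retention.** For a shortfall only at 45 or 60 minutes, section 10.3.3 says "the patient will remain in the study but their insufficient samples will be noted in CDART". Sections 6.2.5 and 8 agree, provided "s/he produced sufficient baseline, immediate, 15 minute and 30 minute post-rinse samples".

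**Populations.** Section 9.3 opens with "Our population includes patients 18-65 years old who have tested positive with COVID-19 in the prior 10 days" and goes no further than eligibility. Sections 9.4 and 9.5 name no analysis set and no handling of missing samples.

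**Analyses affected.** Sections 9.1 and 9.5 compare rinses on viral RNA and infectivity over the time course, through a before/after reduction factor and ANCOVA on the log scale. The primary hypothesis (sections 1.1 and 9.4.1) concerns a reduction lasting at least 30 minutes.

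**The concern.** Randomisation makes the three arms comparable at the moment of assignment. Here, membership of the compared groups also depends on saliva volume after the assigned rinse, at the time points that carry the primary hypothesis. If a rinse changed flow, or willingness to go on giving samples, those retained would differ between arms for reasons other than the rinse's effect on virus. Replacement restores the headcount but not the original comparison.

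Data are also lost. A participant removed at 30 minutes has already given baseline, 0- and 15-minute samples, and the samples still due are never taken. Section 10.3.3 says all saliva samples are assayed, but no section says whether results from removed participants enter the analysis. With no set fixed in advance, that choice could be made after the product key is released. Section 9.4 says the committee evaluating the results will not be masked.

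**Working it through.** **1. The plan's own figure.** Section 9.2 starts from 43 per rinse, allows 14% for no virus and 10% for insufficient saliva, and enrols 55 per arm. The 43 is taken here as stated.

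- Multiplying the retention rates: 43 / (0.86 × 0.90) = 55.6.
- Adding the losses: 43 / (1 − 0.24) = 56.6.
- Using the 14% alone: 43 / 0.86 = 50.

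The stated 55 is close to the first two and needs the saliva allowance. (Section 9.5 gives the same 55 but cites only the 14%.) As sized in section 9.2, the plan therefore allows for insufficient saliva and then replaces the same participants.

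**2. How many are affected.** The 10% is a planning rate, not a ceiling, and is not split into pre-rinse and post-rinse failures. Sections 2.2, 9.1 and 9.2 attach it to 55 per arm; applying it to the 84 per arm in the Précis and section 3 is an assumption.

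- If 84 are to be retained per arm: 84 / 0.90 = 93.3 randomised, about 9 removed.
- If half of the failures are post-rinse (an assumption): 84 / 0.95 = 88.4, about 4 removed after rinsing. Half may be too high, because 5 mL in 5 minutes is required before the rinse and only 2 mL in 5 minutes afterwards.

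**3. Evaluable numbers without any replacement.**

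- From 55: 55 × 0.86 × 0.90 = 42.6, just under 43.
- From 84, if the same allowances apply: 84 × 0.86 × 0.90 = 65.0.

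These are pessimistic for the fix below, which still allows pre-rinse replacement and keeps a participant's other time points when one sample is short.

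**4. Possible bias.** The documents give no removal rates by arm and no correlation between flow and titre, so every input here is assumed. Let flow be standard normal, with the lowest fraction p removed. Mean flow among those kept is m(p) = φ(z_p) / (1 − p).

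- m(0.10) = 0.1755 / 0.90 = 0.195.
- m(0.05) = 0.1031 / 0.95 = 0.109.
- Difference between arms: D = 0.086.

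Let rb and rp be the correlations of flow with baseline and post-rinse log10 titre, and ρ the pre/post correlation (0.5 to 0.7), with equal SDs. The bias in SDs of log10 titre is (rp − rb) × D for the reduction factor and about (rp − ρ × rb) × D for ANCOVA.

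| rb | rp | Reduction factor | ANCOVA |
|---|---|---|---|
| 0.3 | 0.3 | 0 | 0.008 to 0.013 |
| 0.5 | 0.5 | 0 | 0.013 to 0.022 |
| 0.3 | 0.5 | 0.017 | 0.025 to 0.030 |
| 0.5 | 0.3 | −0.017 | −0.004 to 0.004 |

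A simulation with 1,000,000 per arm agrees within 0.005 SD. With equal, like-for-like removal D = 0, and so is the bias.

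**The case against.** The strongest reply is that almost nothing follows in practice. Collectors are blinded (sections 6.2.2, 6.2.3 and 9.2). Volume is read from marked tubes (section 10.3.3). The hardest saliva demand comes before the rinse. Section 6.2.5 attributes these removals to dry mouth that the participant did not know about. The sizing rests on a within-rinse paired test, and the hypothesis concerns within-patient reduction, where selection matters less. All of this stands and is why the estimate of bias is small. It does not restore the randomised comparison between rinses, which sections 9.1 and 9.5 also plan.

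A second reply is that removal may only mean that collection stops, since section 10.3.3 has all samples assayed. That narrows the gap: the documents do not support a reading that samples already collected are thrown away. But assay is not inclusion in an analysis, and the plan is silent on the latter.

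A third is that retention recovers only part of the loss. The short sample is still missing, for a reason related to flow, and its use needs a missing-at-random assumption. That is correct, and the assumption should be stated.

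A reader might infer that the rule materially biases the trial, for example by supposing 20% removal in one arm and 5% in another. The documents do not support this. They show no effect of any rinse on flow, and 20% is twice the plan's whole allowance for insufficient saliva, before or after the rinse.

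**Conclusion.** The point holds as a weakness of design and definition. The rule is explicit in three sections, acts after randomisation and rinsing, falls within the primary 30-minute window, and is not offset by any analysis set in section 9.3. Under the assumptions above (10% versus 5% removal, correlations of 0.3 to 0.5), the bias is about 0 for the reduction factor when the two correlations are equal and about 0.02 SD in size when they differ by 0.2. Under ANCOVA it is about 0.01 to 0.03 SD in most cases and close to zero when flow is more strongly related to baseline than to post-rinse titre. The true size is unknown. It would be wrong to conclude that the results would be invalid, or that a rinse is known to cause removal. The case for change is that randomised data are lost without need and the analysed group is not fixed in advance, while the remedy is cheap.

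**What to change.** **Sections 6.2.5, 8 and 10.3.3.** After the rinse, do not remove or replace anyone for saliva volume. Apply the existing 45/60-minute rule to 0, 15 and 30 minutes: the participant stays, the short sample is recorded as missing for that time point, and what was collected is assayed where volume allows. Withdrawal for safety or at the participant's request is unchanged, and replacement for failing the pre-rinse sample can stay. Any remaining wording should be aligned: sections 6.2.5 and 8 join the early time points with *and*, section 10.3.3 with *or*. The retention sentence shows that the same rule is meant.

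**Section 9.3.** Define the primary set as all randomised participants who rinsed. If those without virus are to be left out, as the 14% allowance implies, define this from the pre-rinse sample only. Keep the current set (sufficient baseline to 30-minute samples) as a sensitivity analysis.

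**Section 9.5.** Analyse all available samples with the planned baseline-adjusted log-scale ANCOVA at each time point, or its repeated-measures extension, and state the missing-at-random assumption. Report short samples by arm and time point, and pre-rinse replacements by arm. Section 10.3.3 already has shortfalls entered in CDART by time point, so this needs no new data.

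**Sample size.** Reconcile 55 per arm (sections 2.2, 9.1, 9.2 and 9.5) with 84 per arm (Précis and section 3), and say which allowances apply.

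**Cost.** Wording changes and an IRB modification, plus a gift card for each participant now retained. There is no extra visit or assay type. Some profiles will be incomplete, and some participants with late-discovered dry mouth will be in the primary set.

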10.3.4 Protocol Deviations

Protocol deviations will be recorded within the source documentation for each participant within the CDART study database by study personnel during the study visits. The investigators and study coordinators will meet weekly to review unanticipated problems, adverse events and protocol deviations recorded in the CDART study database. All such events will be appropriately reported to the IRB board of UNC.

10.3.5 Monitoring

Findings of the site Quality Assurance Coordinator (QAC) will be presented to the investigators and study coordinators (as appropriate for the findings) at selected weekly meetings for discussions and remediation actions as appropriate. The QAC and the lead study coordinator will make recommendations to the PI if needed outside of the regularly weekly study team meetings.

11. PARTICIPANT RIGHTS AND CONFIDENTIALITY

11.1 Institutional Review Board (IRB) Review

This protocol and the informed consent document and any subsequent modifications will be reviewed and approved by the IRB or ethics committee responsible for oversight of the study. Consent forms are separate from this protocol document and were submitted as part of the IRB application.

11.2 Informed Consent Forms

Patients who have tested positive for COVID-19 in the UNC Respiratory Diagnostic Clinic (RDC), UNC testing sites or UNC hospital will be contacted to participate in this study by research personnel. Patients will be contacted first by phone and, if not available, then by email. The study's purpose and requirements will be explained and the

patient will have the opportunity to ask questions and will have time to consider participation. Interested patients will make an appointment to visit the clinical isolation area associated with the Go Health Clinical Research Unit at Adams School of Dentistry for this study. Study participation includes only one visit. The consent forms will be reviewed and signed by interested patients in person in the isolation area adjacent to the Go Health Clinical Research Unit at Adams School of Dentistry.

For hospital in-patients appearing on the EPIC COVID+ list, subjects will be approached by a study coordinator in their private room. The study's purpose and requirements will be explained and the patient will have the opportunity to ask questions and will have time to consider participation. If interested, consent forms will be left in the patient's room for review. Study team members will return later for final consent signatures and if consenting, the study visit can occur in the patient's room.

A signed consent form will be obtained from each participant. For participants who cannot consent for themselves, such as those with a legal guardian (e.g., person with power of attorney), this individual must sign the consent form, though minors and patients who are intellectually delayed and unable to consent for themselves will be excluded. The consent form will describe the purpose of the study, the procedures to be followed, and the risks and benefits of participation. A copy will be offered to each participant or legal guardian and this fact will be documented in the participant's record. For Spanish speaking patients and/or parents, Spanish forms will be provided and communication will occur through a Spanish translator. All patients are adults and over normal cognitive capacity, and therefore will be able to consent for themselves.

At the visit, a consented patient will answer screening questions regarding inclusion and exclusion criteria. Answers will be entered into the CDART research database managed by UNC. Prior to finalizing these screening questions, women participants of childbearing potential will be asked to provide a urine sample in the restroom, to undergo a rapid pregnancy test by study personnel. Any pregnant or lactating patients will be excluded.

Our study statistician will create a block randomization tool and the unblinded staff member will randomize participants. All patients will be consented and then answer our screening questions for inclusion and exclusion to confirm eligibility prior to being assigned to the randomization schedule.

